1 STUDY SYNOPSIS

Complete Protocol Title	Anaverse [™] Glenoid System and its instrumentation - Retrospective and Prospective, Non-Controlled Post Market Clinical Follow-Up Study
Protocol Number	CME2017-11E
Short Protocol Title	Anaverse [™] Glenoid System and its instrumentation
Sponsor	Zimmer GmbH, [name]
Manufacturer	Zimmer Switzerland Manufacturing GmbH, [name]
Study Device(s)	Anaverse [™] Glenoid System
Study Objectives/Endpoints	The objectives of this study are to confirm safety, performance and clinical benefits of the Anaverse™ Glenoid System and its instrumentation by analysis of standard scoring systems, radiographs and adverse event records. The safety of the system will be assessed by monitoring the frequency and incidence of adverse events. The performance and clinical benefits will be evaluated by assessment of the overall pain and functional performance, survival, and radiographic parameters of all enrolled study subjects. The primary endpoint is defined by the survival of the implant system at 2 years which is based on removal or intended removal of the Anaverse™ Glenoid System baseplate and will be determined by using the Kaplan Meier method.
Indications/Target Population	Patients suffering from severe shoulder pain and disability indicated for implantation of the Anaverse™ Glenoid System in cases of total shoulder arthroplasty in reversed configuration. Patients who underwent total shoulder arthroplasty conversion from anatomical to reversed will be enrolled for subgroup analysis. Patients must meet all inclusion and none of the exclusion criteria. The reversed configuration of the Anaverse Glenoid System is indicated for patients with significant shoulder disability due to gross and irreparable rotator cuff deficiency. A functional deltoid muscle is necessary to use the device. The conversion from anatomical to reversed configuration is indicated for patients that were implanted with the system in the anatomical configuration and that present irreparable rotator cuff and superior migration of the humeral head, leading to a reduction in sub-acromial space.
Inclusion/Exclusion Criteria	Inclusion and exclusion criteria reflect indications and contraindications reported on the device instructions for use (IFU).

Inclusion criteria:

- Patient is 18-75 years of age, inclusive.
- Patient is skeletally mature.
- Patient is capable of understanding the doctor's explanations, following his instructions and is able to participate in the follow-up program.
- Patient must have signed EC-approved informed consent.
- Patient requires a primary reversed total shoulder arthroplasty or a conversion from anatomical to reversed to relieve pain and restore the joint function.
- Patient has adequate quality and quantity of bone stock to support the prosthesis.
- Patient meets at least one of the following indications:
 - Advanced wear and tear of the shoulder joint resulting from degenerative, posttraumatic or rheumatoid arthritis
 - Conditions consequent to earlier operations
 - Omarthrosis or Osteoarthritis
 - Rheumatoid arthritis
 - Total joint reconstruction following trauma
- Patient has significant shoulder disability due to gross and irreparable rotator cuff deficiency. A functional deltoid muscle is necessary to use the device.
- Patient underwent reverse total shoulder reconstruction with the Anaverse Glenoid System before the date of site initiation.
- Patient has demographic, pre-operative evaluation, operative report and device information available.

Specific inclusion criteria for Conversion from Anatomical to Reversed Configuration:

- Surgery was performed with the Anaverse Glenoid System in a previously available anatomical configuration.
- Irreparable rotator cuff with superior migration of the humeral head, leading to a reduction in sub-acromial space.
- Superior tilt of the Anaverse Glenoid Baseplate not exceeding 15° compared to scapular axis.

No evidence of mechanical or fixation failure of the Baseplate, TM Pegs or DPSC Screws, obtained pre- or intraoperatively, which would compromise the success of the conversion surgery.

Exclusion criteria:

- Patient is unwilling or unable to give consent or to comply with the follow-up program.
- Patient has any condition which would in the judgment

	of the Investigator place the patient at undue risk or interfere with the study. Patient is known to be pregnant or breastfeeding. Patient is a vulnerable subject (prisoner, mentally incompetent or unable to understand what participation to the study entails, a known alcohol or drug abuser, anticipated to be noncompliant). Patient has any physical conditions that would impair adequate implant support and/or prevent the use of an appropriately sized implant. Patient has any sign of infection (affecting the shoulder joint or in its proximity). Patient has glenoid presenting with large defects due to erosion, which would lead to insufficient bony support or malalignment of the devices. Patient is skeletally immature. Patient has any sign of neuromuscular compromise (excluding rotator cuff tear). Patient has vascular deficiency in the affected limb in sufficient degree to endanger the success of the intervention. Patient has absence of musculo-ligamentous supporting structures. Patient suffers from joint neuropathy or other conditions that may lead to inadequate skeletal fixation. Patient has significant injury to the upper brachial plexus. Patient has non-functional deltoid muscle. Specific exclusion criteria for Conversion from Anatomical to Reversed Configuration: Unstable fixation of Baseplate after removal of PE Liner. Superior tilt of Baseplate exceeding 15° compared to scapular axis Superior malposition of the Baseplate which would prevent correct assembly of the Glenosphere. Evidence of mechanical or fixation failure of the Baseplate, TM Pegs or DPSC Screws, obtained pre- or intra-operatively, which would compromise the success of the conversion surgery.
Study Design	Retrospective and prospective, non-controlled post market surveillance study.
Clinical Phase	Post-market
Sample Size	30 shoulders.

	2
Length of Study	3 years (1 year of enrollment plus 2 years of follow-up): follow-up visits at 6 weeks, 1 and 2 years postoperatively.
Materials and Methods	Case report forms will be completed either in-office or hospital at Pre-op, Surgery, Discharge, and at the 6 weeks, 1 year, and 2 year post-operation intervals.
Data Collection	Paper/Electronic
Statistical Reporting	Data collected will be summarized and reported to each participating investigator. Statistical analysis will be conducted by Zimmer Biomet or its designee. Survivorship will be evaluated using Kaplan-Meier. Categorical data, such as incidences and device-related complications, will be summarized using counts and percentages with 95% confidence intervals. Continuous data, such as patient satisfaction scores, will be summarized by using means, medians, standard deviations, minimum, maximums, and 95% confidence intervals. Patient demographics, such as age and gender, will also be similarly summarized and reported on. Patients who underwent reoperations and/or revisions of components other than the baseplate will also be included in the statistical analysis. This subpopulation is not statistically powered; however, it will be included in the statistical analysis. Statistical analyses will be performed using SAS 9.4. The binomial distribution tests will have 80% probability of computing a two-sided 90% confidence interval on survivorship of each device with a non-inferiority margin of 0.09.
Scores/Performance Assessments	Constant-Murley, Patient Satisfaction, Revisions, Adverse Events, Radiographic Assessment.
Standards	 The PMCF is compliant with the below: ISO 14155: 2020 - Clinical investigation of medical devices for human subjects - Good clinical practice. The Declaration of Helsinki (DoH) – Ethical principles for medical research involving human subjects. European Regulation (EU) 2017/745.
Study Funding	Funding for this clinical study is made available by Zimmer Biomet to support clinical data collection, IRB/EC review fees and other expenses associated with the conduct and execution of this study protocol as outlined in the fully executed Clinical Trial Agreement

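### Is it unclear whether conversion shoulders count in the 30 and in the primary survival estimate, and when their 2-year clock starts?

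*Combined protocol and SAP*

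**What the plan says.** All references are to section 1, Study Synopsis.

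- **Study Objectives/Endpoints.** "The primary endpoint is defined by the survival of the implant system at 2 years which is based on removal or intended removal", where the component is the baseplate and the method is Kaplan-Meier. The sentence before this one says that performance and benefit, with survival named among the measures, are assessed in everyone enrolled.
- **Indications/Target Population.** The device is studied in its reversed configuration. "Patients who underwent total shoulder arthroplasty conversion from anatomical to reversed will be enrolled for subgroup analysis".
- **Inclusion criteria, common list.** "Patient requires a primary reversed total shoulder arthroplasty or a conversion from anatomical to reversed to relieve pain and restore the joint function". The same list requires that a reverse reconstruction with this system took place before the site was initiated.
- **Inclusion criteria for conversions.** "Surgery was performed with the Anaverse Glenoid System in a previously available anatomical configuration". Mechanical failure that would endanger the conversion is ruled out, and so is "fixation failure of the Baseplate, TM Pegs or DPSC Screws, obtained pre- or intraoperatively, which would compromise the success of the conversion surgery".
- **Sample Size.** 30 shoulders, with no split by type of operation.
- **Length of Study.** "follow-up visits at 6 weeks, 1 and 2 years postoperatively".
- **Statistical Reporting.** For shoulders with reoperation or revision of other components: "This subpopulation is not statistically powered; however, it will be included in the statistical analysis". Conversions get no matching sentence. The test is described with 80% power, a two-sided 90% interval and a margin of 0.09.

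**The concern.** Two things appear to be left open. The first is membership. Enrolling patients for a subgroup analysis could mean a subset of the 30 or a group beside them, and the endpoint sentence names no analysis set. The synopsis settles the matter for the reoperation subpopulation, which makes its silence on conversions stand out.

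The second is time zero. The event is removal of the baseplate. In a conversion that baseplate was put in at the anatomical operation and kept, after a check that it was sound. A conversion shoulder therefore has two operations that could start the clock, and the word postoperatively does not choose between them.

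If both were truly open, the analyst could choose the set and the clock after seeing the data. With few events expected in 30 shoulders, that choice could move the lower confidence limit by an amount that matters against a margin of 0.09. A primary-only set would also be smaller than 30 and so have less power.

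**Working it through.** **1. Membership.** Three statements bear on it and agree. Survival is assessed in everyone enrolled, and conversions are enrolled. The common list admits "Patient requires a primary reversed total shoulder arthroplasty or a conversion from anatomical to reversed" as alternatives in one cohort. The total of 30 is undivided. A subgroup is ordinarily part of the group. Only the phrase about enrolling for subgroup analysis could suggest a separate group, and it does not say so.

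**2. Time zero.** The common list requires a reverse reconstruction, and for a conversion shoulder that is the conversion. Conversion eligibility is partly judged during that operation, for example by whether the baseplate is stable once the liner is out. A clock started at the anatomical operation would credit time during which the baseplate could not have been removed, since a removal would have ruled the shoulder out. No text proposes that clock.

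**3. The stated sample size.** The documents give no expected survival p. With n = p(1-p)(1.645 + 0.842)²/0.09², p = 0.96 gives 0.0384 × 6.18/0.0081 = 29.3, rounded up to 30. p = 0.95 gives 37 and p = 0.97 gives 23. So 30 fits an assumed 96% but is not confirmed by it. I use 96% below as an assumption.

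**4. Shift in the estimate from pooling.** With k conversions of survival s among 30, pooled minus primary-only is k(s - 0.96)/30. The values of k and s are assumptions.

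| k | s = 0.90 | s = 1.00 |
|---|---|---|
| 3 | -0.6 points | +0.4 points |
| 5 | -1.0 | +0.7 |
| 10 | -2.0 | +1.3 |

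**5. Shift from the clock.** With a constant hazard and a gap of g years before conversion, survival in conversions counted from the anatomical operation would be 0.96^(1 - g/2). That is 97.0% at g = 0.5, 98.0% at 1, 99.0% at 1.5 and 100% at 2 or more. Carried into 30 shoulders, 3 conversions move the estimate by 3/30 × 1.0 = 0.1 points (g = 0.5) to 3/30 × 4.0 = 0.4 points (g of 2 or more). With 10 conversions the most is 10/30 × 4.0 = 1.3 points.

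**6. Lower limits of the two-sided 90% interval (exact).**

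| Assumed case | Primary-only | Pooled | Difference |
|---|---|---|---|
| 3 conversions, one removal in a primary | 26/27: 83.6% | 29/30: 85.1% | 1.5 points |
| 3 conversions, one removal in a conversion | 27/27: 89.5% | 29/30: 85.1% | 4.4 |
| 10 conversions, one removal in a primary | 19/20: 78.4% | 29/30: 85.1% | 6.7 |
| 10 conversions, one removal in a conversion | 20/20: 86.1% | 29/30: 85.1% | 1.0 |

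Part of each difference comes from the smaller sample and not from bias.

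**7. Power.** Φ(0.09/√(0.0384/n) - 1.645) is 80.8% at n = 30, 77.1% at 27, 74.3% at 25 and 65.9% at 20. The losses arise only if conversions count in the 30 but are left out of the primary estimate. On the natural reading n stays at 30.

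**The case for a change.** The strongest case is that likely is not the same as stated, and this is the primary endpoint. The sentence about everyone enrolled is general and comes before the endpoint definition. The operations precede site initiation, so some outcomes may be known before the analysis, which is when the set and the clock should already be fixed. An extreme example can be built. Take 24 primaries and 6 conversions, with two conversion baseplates removed one year after conversion and three years between the two operations. Two-year survival is then 28/30 = 93.3% (exact lower limit 80.5%) from the conversion, and 100% (90.5%) from the anatomical operation. That is 10 points, more than the margin.

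Part of this stands. The synopsis has no express sentence on either point, and such a sentence would cost little. But the 10 points need a clock that no passage supports and that counts time in which the event could not happen. The 6.7 points and the power losses need a primary-only set, the reading the text favours least, and in the case of the 6.7 points also 10 conversions of 30. The inputs to these examples (number of conversions, their survival, the gap between operations) are not in the documents. The planned subgroup analysis would also show the conversions separately, so their influence on a pooled figure would be open to view.

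**Conclusion.** This is a gap in wording that analysts would fill sensibly: conversions count within the 30, enter the Kaplan-Meier estimate and are timed from the conversion surgery. Followed that way, the plan gives a sound estimate of baseplate survival in the reversed configuration. Naming a primary-only set would also be defensible, but it would bring no clear gain and would reduce the sample. The effect on the primary result cannot be sized from the documents. Under the assumed 96%, and 90% to 100% in conversions, pooling shifts the estimate by at most 2.0 points with as many as 10 conversions, and by at most 0.6 with 3. The lower limit can move further, by 1.0 to 6.7 points in the set-membership cases shown, but only against a reading that the text does not favour. The conclusion rests on the synopsis, the only part of the plan available for this review. No change is needed.

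### Shoulders are selected after surgery, and the synopsis does not say whether baseplates already removed at consent are enrolled, so 2-year survivorship could be overstated

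*Combined protocol and SAP*

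**What the plan says.** All places are in section 1, Study Synopsis, the only part of the protocol supplied.

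- **Indications/Target Population:** the criteria are cumulative: "Patients must meet all inclusion and none of the exclusion criteria".
- **Inclusion criteria:** one criterion fixes the timing of surgery: "Patient underwent reverse total shoulder reconstruction with the Anaverse Glenoid System before the date of site initiation". Another requires consent: "Patient must have signed EC-approved informed consent". Ability to take part in follow-up is required as well.
- **Exclusion criteria:** "Patient is unwilling or unable to give consent or to comply with the follow-up program".
- **Study Objectives/Endpoints:** "The primary endpoint is defined by the survival of the implant system at 2 years which is based on removal or intended removal" of the baseplate, estimated by Kaplan-Meier. Performance is assessed in "all enrolled study subjects".
- **Statistical Reporting:** "Survivorship will be evaluated using Kaplan-Meier". The one sentence about revised patients is: "Patients who underwent reoperations and/or revisions of components other than the baseplate will also be included in the statistical analysis".
- **Study Design, Sample Size and Length of Study:** a retrospective and prospective study without controls, 30 shoulders, one year of enrolment and two of follow-up, with visits at 6 weeks, 1 year and 2 years after surgery.

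The synopsis contains no consecutive-enrolment rule, no log of implanted shoulders, no statement on baseplates removed before consent, and no delayed-entry rule for the Kaplan-Meier analysis.

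**The concern.** Taken together, the criteria admit only shoulders implanted before the site opened, whose patients then consent. Time passes between implantation and consent, and some baseplates may be lost in it. A patient whose device is already out has less reason to join a follow-up programme for it and may have moved to other care. That is a plausible mechanism, not something the documents report.

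If removed shoulders enter less readily than surviving ones, the sample is selected on the outcome. Kaplan-Meier started at surgery would then credit the survivors with a period in which, by the way they were chosen, they were less likely to fail. The error favours the device and affects the primary endpoint of a single-arm study with no comparator to expose it. Without counts of implanted and enrolled shoulders, a reader of the results cannot tell whether this happened.

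**Working it through.** **Plan's own figure.** The plan states neither an expected removal rate nor a surgery-to-consent interval, so there is no bias figure to reproduce. What follows is an illustration.

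**Inputs from the documents.** n = 30 shoulders; event = baseplate removal or intended removal; horizon 2 years.

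**Assumed inputs.**
- True 2-year failure F(2) = 4%. The plan does not give this. It is the complement of the survivorship at which one common sample-size formula returns 30: 0.96 × 0.04 × (1.645 + 0.842)² / 0.09² = 29.3, rounded up to 30. Other variants give 64 or 68 at the same survivorship, so this is not confirmation.
- Entry (consent) time e is uniform over 0–1 or 0–2 years after surgery. After 2 years no scheduled visit remains.
- The hazard is constant (exponential), or early-weighted (Weibull, shape 0.5, with about half of 2-year failures in the first 6 months).
- f is the share of pre-consent removals that are enrolled and counted at their true date.
- There is no censoring before 2 years.

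**Formula.** With m the mean of F(e) over entry times,

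apparent 2-year failure = [F(2) − (1 − f) m] / [1 − (1 − f) m].

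**Share of 2-year failures that precede consent, m / F(2).** Entry 0–1 years: 25.3% (exponential), 47.6% (Weibull). Entry 0–2 years: 50.3%, 67.0%.

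**Worked case.** Exponential, entry 0–1 years: m = 0.253 × 0.04 = 0.0101.
- f = 0: (0.04 − 0.0101) / (1 − 0.0101) = 3.02%.
- f = 0.5: (0.04 − 0.0051) / (1 − 0.0051) = 3.51%.

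| f | 0–1 y, exponential | 0–1 y, Weibull | 0–2 y, exponential | 0–2 y, Weibull | Overstatement of survivorship (points) |
|---|---|---|---|---|---|
| 1 | 4.00% | 4.00% | 4.00% | 4.00% | 0 |
| 0.75 | 3.76% | 3.54% | 3.51% | 3.35% | 0.2–0.7 |
| 0.5 | 3.51% | 3.08% | 3.02% | 2.70% | 0.5–1.3 |
| 0 | 3.02% | 2.14% | 2.03% | 1.36% | 1.0–2.6 |

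**Against sampling error.** Binomial standard error at 4% with n = 30: √(0.04 × 0.96 / 30) = 3.6 points. Every scenario lies below one standard error.

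**Chance of seeing no removal in 30, (1 − p)^30.** At the true 4%: 0.96^30 = 29%. With f = 0.5: 34%–44%. With f = 0: 40%–66%.

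**One missed removal.** If a surviving shoulder takes its place, 29/30 = 96.7% becomes 30/30 = 100%, a shift of 3.3 points. If the true denominator is 31, 30/31 = 96.8% appears as 100%, a shift of 3.2 points. In the second case the exact lower limit of a two-sided 90% interval is 85.6% with the removal counted and 90.5% without it.

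**Delayed entry.** With each shoulder at risk only from consent, on a clock started at surgery, the bias goes if entry is unrelated to later failure. The price is thin early risk sets. Ignoring removals, at 6 months about 30 × 0.5 = 15 shoulders would be at risk with entry over 0–1 years, and 30 × 0.25 = 7.5 with entry over 0–2 years.

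**The case against.** The strongest case on the other side has four parts.

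1. **The text is mostly benign.** No criterion requires the baseplate to be in place at consent. The word *also* in the sentence on other components suggests that baseplate revisions are already counted, and performance is assessed in all enrolled subjects. Visits are timed from surgery, so the clock probably starts there. This stands, and it rules out the stronger reading that the plan excludes failed baseplates or that its estimate is biased. But these sentences describe what happens once a shoulder is enrolled. None says whether an already revised shoulder gets enrolled.

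2. **Only a synopsis is available.** Enrolment logs and the handling of revised patients often sit in the body of a protocol. This stands too: the point is silence in the text supplied, and the full protocol may fill it.

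3. **The shifts are small.** In absolute terms they are 0.5 to 2.6 points, below one standard error, and they rest on differential enrolment that is assumed. This is correct. A reader might note that three missed removals in 33 implanted shoulders would shift the estimate by 9.1 points, about the whole 0.09 margin. Nothing in the documents points to so many: at 4% failure, 30 implanted shoulders would have 30 × 0.04 = 1.2 expected removals by 2 years, of which 0.3 to 0.8 before consent.

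4. **The analysis can help.** A reader might infer that selection after the event is beyond repair. It is not: delayed entry at consent removes the bias if entry is non-informative. What stands is that the synopsis does not specify it and that it would be imprecise here.

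A reader might also infer that the infection exclusion, applied at consent, keeps out infected shoulders that go on to fail. The criteria do not support this. The requirement that the patient need the arthroplasty, and the requirement for a pre-operative evaluation and operative report, both point to clinical eligibility judged before surgery.

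Finally, the retrospective-and-prospective label can mean past surgery with prospective follow-up. That would fit the site-initiation criterion, but the selection would still be made after surgery.

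**Conclusion.** The point holds in conditional form. Read literally, the criteria place selection after the primary event may have occurred, and the synopsis has no enrolment or analysis rule to guard against the consequence. If every pre-consent removal is enrolled and counted at its true date, there is no bias. If removed shoulders are enrolled less often, ordinary Kaplan-Meier from surgery overstates 2-year survivorship, under the stated assumptions by 0.5 to 1.3 points with half enrolled and 1.0 to 2.6 with none.

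These sizes depend on the assumed 4% failure, entry window, hazard shape and enrolment share. In relative terms they hardly change for true failure between 2% and 6%: failure is understated by about 12%–33% with half enrolled and 24%–66% with none. The expected bias is modest beside sampling error, but it runs in one direction and would be invisible in the report. It should be fixed because the remedy is cheap. Confidence is medium, since the full protocol may already deal with it.

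**What to change.** 1. At each site, list all consecutive Anaverse reverse implantations in the eligible period, and offer enrolment regardless of current baseplate status.
2. State that Kaplan-Meier time starts at surgery and that removals before consent count as events at their true date. If they cannot be fully captured, use Kaplan-Meier with delayed entry at consent, dropping pre-consent time and events, as the fallback or a sensitivity analysis. Note that it will be imprecise with 30 shoulders.
3. Report the numbers of implanted, enrolled and non-enrolled shoulders, with the reason for non-enrolment and baseplate status where known.
4. Reconcile the site-initiation criterion with the retrospective-and-prospective label, saying whether shoulders operated on after initiation can enter.

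The cost is a screening log at each site and a few sentences in the eligibility and analysis text. The estimate may come out less favourable, and the status of some non-enrolled shoulders may stay unknown.

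### The only survivorship interval has no type, no reference survivorship and no link to the Kaplan-Meier primary estimate, and its stated 80% does not hold at N=30 with exact limits

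*Combined protocol and SAP*

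**What the plan says.** Under Study Objectives/Endpoints (1 Study Synopsis): "The primary endpoint is defined by the survival of the implant system at 2 years", based on removal or intended removal of the baseplate, and it "will be determined by using the Kaplan Meier method". Statistical Reporting repeats this: "Survivorship will be evaluated using Kaplan-Meier".

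Statistical Reporting mentions intervals in two places. Categorical data, "such as incidences and device-related complications, will be summarized using counts and percentages with 95% confidence intervals", and continuous data likewise get 95% intervals. The row then closes by saying that the binomial tests "will have 80% probability of computing a two-sided 90% confidence interval on survivorship of each device with a non-inferiority margin of 0.09".

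That closing sentence gives a level, a sidedness, a distribution and a margin. It does not say which binomial interval is meant, to what survivorship the 0.09 applies, how shoulders lost before 2 years are counted, or how the interval relates to the Kaplan-Meier estimate. The Sample Size row gives 30 shoulders. The Length of Study row gives "follow-up visits at 6 weeks, 1 and 2 years postoperatively". No loss-to-follow-up rate is stated.

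**The concern.** With 30 shoulders and a low removal rate, the usual large-sample limits for a survival probability break down. Two analysts following the text could report the same data with quite different lower limits, and both would comply. If the margin is then applied to that lower limit, the primary conclusion can turn on which limit was used, and nothing in the text fixes that choice before the removals are known.

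The 80% is the second problem. It is a probability statement about an interval of unstated type against an unstated reference, so it cannot be verified as written. If it fails for a sound interval at any plausible reference, readers are told that the study is more conclusive than it is.

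**Working it through.** **Inputs from the synopsis:** N = 30 shoulders; two-sided 90% interval, so 5% in the lower tail; margin 0.09; probability 80%; Kaplan-Meier at 2 years. **Assumed, because not stated:** reference survivorship (94% to 99% shown, 80% to 99% checked) and no censoring. Without censoring the Kaplan-Meier estimate is S = (30 − d)/30 for d removals, and Greenwood's standard error is √(S(1 − S)/30), so the linear Greenwood limit equals the Wald limit.

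**1. Can N = 30 be reproduced?** Not from stated inputs. The one-sample Wald formula is n = p(1 − p)(1.645 + 0.842)²/0.09².
- p = 0.95: 36.3, rounded up to 37
- p = 0.96: 29.3, rounded up to 30
- p = 0.97: 22.2, rounded up to 23

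So 30 fits this formula at an assumed 96%. The synopsis does not say that this was the route.

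**2. How likely are zero or one removals?** P(0) = p³⁰ and P(1) = 30p²⁹(1 − p).
- p = 0.95: 0.215 + 0.339 = 55%
- p = 0.96: 0.294 + 0.367 = 66%
- p = 0.98: 0.545 + 0.334 = 88%
- p = 0.99: 0.740 + 0.224 = 96%

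**3. Lower 90% limits at n = 30.**

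| Removals | Linear/Wald | Log | Log-log | Wilson | Exact |
|---|---|---|---|---|---|
| 0 | 1.000 | 1.000 | undefined | 0.917 | 0.905 |
| 1 | 0.913 | 0.914 | 0.839 | 0.864 | 0.851 |
| 2 | 0.858 | 0.861 | 0.802 | 0.817 | 0.805 |

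At zero removals S = 1 and the standard error is 0, so linear and log limits run from 100% to 100%. The log-log transform does not exist. The exact limit is 0.05^(1/30) = 0.905. At one removal S = 0.967 and the standard error is 0.0328. The linear lower limit is 0.967 − 1.645 × 0.0328 = 0.913, and the upper limit is 1.021, above 1. Coverage of the nominal 90% linear interval is 77%, 70% and 45% at true survival 95%, 96% and 98%. The exact interval covers 97% to 98%.

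**4. Does the 80% hold?** Count a pass when the lower limit exceeds reference − 0.09. The chance of passing takes true survival equal to the reference. False passing takes true survival equal to reference − 0.09 (nominal 5%).

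| Assumed reference | Threshold | Exact: most removals that pass | Exact: chance of passing | Exact: false pass | Wald: most removals that pass | Wald: chance of passing | Wald: false pass |
|---|---|---|---|---|---|---|---|
| 94% | 0.85 | 1 | 46% | 4.8% | 2 | 73% | 15.1% |
| 95% | 0.86 | 0 | 21% | 1.1% | 1 | 55% | 6.4% |
| 96% | 0.87 | 0 | 29% | 1.5% | 1 | 66% | 8.4% |
| 97% | 0.88 | 0 | 40% | 2.2% | 1 | 77% | 11.0% |
| 98% | 0.89 | 0 | 55% | 3.0% | 1 | 88% | 14.3% |
| 99% | 0.90 | 0 | 74% | 4.2% | 1 | 96% | 18.4% |

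From 95% to 99% only 30/30 passes with exact limits (0.851 is below 0.86; 0.905 is above 0.90), so the chance is p³⁰. Over references from 80% to 99% the exact chance never exceeds 74%. At 96%, where the Wald formula returns 30, the Wald limit itself gives 66%. It reaches 80% only at the highest references shown, and there its false-pass rate is 14% or more.

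**5. Another reading of the sentence.** If it means an 80% probability that the interval reaches no more than 0.09 from the estimate, Wald gives 81% at an assumed 95%. The exact lower limit lies 1 − 0.905 = 0.095 below the estimate even with zero removals, and further below with one, two or three (0.115, 0.129, 0.139). Enumeration gives 0% at every survival checked from 93% to 98%.

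**The case against.** The strongest reply is that the synopsis is not silent. It names a "two-sided 90% confidence interval on survivorship of each device" under a binomial distribution, and it does so under Statistical Reporting, not in the Sample Size row. If an exact binomial interval is meant, 30/30 gives 0.905 to 1.000 and nothing collapses. That is right, and a reader who infers that the plan has no survivorship interval at all goes too far. What stands is narrower: Wald limits are also binomial, so the distribution alone does not settle the type, and no sentence ties the interval to Kaplan-Meier.

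A reader might also infer that the plan will use Greenwood, linear or Wald limits. It names none of them; they are choices left open, and reporting 100% to 100% is a possibility, not a plan.

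A third tempting inference is that 30 is too small and must be raised. The documents do not support that either. Every pass or fail above rests on an assumed reference, and without a stated one there is no verdict to reverse. The log limit does reach 81% at an assumed 95%, but with a false-pass rate of 18.9%.

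Finally, only the synopsis was available, and interval detail often sits in a fuller statistical section. If that section names the method and reference, the first part of this point is answered. The 80% would still need checking against what is named there.

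**Conclusion.** The point holds as an incomplete specification with a real consequence, and it should be fixed. The primary estimate has no interval tied to it, and the one survivorship interval given lacks a type and a reference. At zero removals (21% to 74% likely at assumed survival of 95% to 99%) Greenwood limits are unusable. At one removal the linear limit is 0.062 higher than the exact one (0.913 − 0.851).

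The stated 80% is not supported by exact limits at any reference from 80% to 99% when true survival equals the reference; the most they give is 74%. This conclusion does not depend on picking one reference within that range, but it does depend on reading the sentence as the chance of meeting the margin, and on no censoring. Random loss to follow-up and the delayed entry of shoulders operated on before site initiation are not reflected in these figures. Confidence is medium, because the text available is a synopsis.

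**What to change.** In Statistical Reporting:

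1. State that the primary result is the 2-year Kaplan-Meier estimate with a two-sided 90% beta product interval. Without censoring this equals Clopper-Pearson, it is defined at zero removals, and it accommodates censoring. Rule out linear, log and Wald limits. Name only one method: at an assumed 94% (threshold 0.85), one removal passes with beta product (0.851) and fails with log-log (0.839), so offering alternatives would reopen the choice.
2. State the reference survivorship to which 0.09 applies, and base the conclusion on that one lower limit.
3. Say what the binomial sentence is for, and replace the 80% with the probability that N = 30 gives for this interval and reference.

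The text and programming changes are small. The real cost is less favourable reporting (a lower limit of 0.905 instead of 1.000 at 30/30) and a stated probability well below 80%, for example 29% at an assumed 96%. Whether to change N is a separate decision that can be taken once the reference is stated.
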